### **9.3. Endpoints**

#### **9.3.1. Primary Endpoints**

- Overall Response Rate (ORR)**

Overall response rate (ORR) is defined as the proportion of participants having a complete (CR) and partial (PR) response.

#### **9.3.2. Secondary Endpoints**

- Duration of response (DOR)**

Duration of response is measured from date of documented tumor response, CR or PR, to date of disease progression.

- Progression Free Survival (PFS)**

Progression-free survival is measured from date of study entry to date of progression or death, whichever occurs first.

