	
 
• Requires treatment with a strong cytochrome P450 (CYP) 3A4/5 inhibitor. (see Appendix 3)
 
• Currently active, clinically significant hepatic impairment Child-Pugh class B or C according to the Child Pugh classification
 
• Lactating or pregnant.
 
• Unwilling or unable to participate in all required study evaluations and procedures.
 
• Unable to understand the purpose and risks of the study and to provide a signed and dated informed consent form (ICF) and authorization to use protected health information (in accordance with national and local subject privacy regulations).
 

Study Treatment:	Ibrutinib 560mg p.o. q.d. until disease progression, unacceptable toxicity or patient/clinician choice to discontinue.
Concomitant Therapy:	Refer to Section 6 for information on concomitant therapy.
Safety Plan:	The Barbara Ann Karmanos Cancer Institute, Data and Safety Monitoring Committee (DSMC), provides the primary oversight of data and safety monitoring for KCI Investigator-initiated trials. In Addition monthly investigator teleconferences will occur to discuss adverse event and safety issues.
Statistical Methods and Data Analysis:	
All efficacy analyses will be performed using all evaluable participants.
 
Primary Efficacy Analysis:  A one-sample binomial test will be used to assess efficacy in terms of ORR. The ORR will be reported as a proportion with a one-sided, lower 95% confidence interval. Assuming p0=30%, pA=50%, power=85% and type I error = 10.69% the null hypothesis will be rejected if there are 13 or more ORRs.
 
Secondary Efficacy Analysis:  DOR will be reported as median and range. Kaplan-Meier estimate of median PFS will be reported with 95% confidence intervals.
 
Exploratory Efficacy Analysis:

	
The influence of ibrutinib on T cell behavior and antitumor effect will be assessed using a variety of techniques including gene expression and mutational analysis. T cell subset alterations in blood and tumor tissue will be analyzed and PD-1 and PD-2 expression will be evaluated by FISH and IHC.
 
Safety Analysis:
 
Frequency of grade 3 or higher adverse events will be tabulated and all grade 1 and 2 adverse events will be collected.

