disease progression, death or study end, whichever comes first. Subjects off treatment will be contacted every 9 weeks to obtain data on subsequent anti-HL therapies (including treatment regimen, start date, end date, and best response to subsequent therapy) and survival status. If the information on subsequent anti-HL therapies and survival status is obtained via telephone contact, written documentation of the communication must be available for review in the source documents. If the subject has died, the date and cause of death will be collected and documented on the CRF.

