## 7.3 Evaluations

### 7.3.1 Radiographic Image Assessments

During the study, disease response will be assessed using whole body FDG-PET scans and CT scans with IV contrast of the neck, chest, abdomen, and pelvis and any other location where disease was present at screening. Subjects who are intolerant of IV CT contrast agents will have CT scans performed with oral contrast. A separate CT scan and PET scan are preferred but, if the only available modality is combined/dual PET/CT scanner, then the CT portion of a PET/CT may be performed in lieu of a dedicated CT; however, the CT scanning must be done with contrast 1 to ensure that an optimized CT examination is done. Evaluation of other sites of disease by radiological imaging, physical examination, or other procedures as necessary (to be performed throughout the study using the same method of assessment used to assess disease at

baseline), and review of hematology and clinical chemistry results may be performed at the site level, as determined by the investigator. Magnetic resonance imaging may be used to evaluate sites of disease that cannot be adequately imaged using CT (in cases where MRI is desirable, the MRI must be obtained at baseline and at all subsequent response evaluations). For all other sites of disease, MRI studies do not replace the required neck, chest, abdomen, and pelvic CT scans. Brain MRI and lumbar puncture are required, only if clinically indicated.

Radiological assessments will be performed at Screening, (PET and CT w/ contrast) upon completion of cycle 2 (week 8 PET and CT w/ contrast). Thereafter, CT with contrast will be performed every 12 weeks until disease progression, death, or end of study, whichever comes first. Patients who remain on study without progression at 15 mos. may have subsequent imaging performed every 24 weeks. A PET scan will be performed at Screening and after cycle 2 and at CR. PET scans will also be done at the time of maximal tumor reduction (eg, CR or 2 consecutive CT scans showing no further tumor reduction), relapse from CR, and at suspected disease progression if new lesion was detected on CT.

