Subjects who discontinue treatment prior to disease progression (for other reasons such as an adverse event) must continue to have regularly scheduled CT scans/efficacy assessments every 12 weeks up to 15 months after the start of study drug. Thereafter, scan will be performed every 24 weeks until disease progression, or death, or the end of the study, whichever occurs first. It is important that instances of progressive disease be reported to the lead investigators at Karmanos Cancer Institute within 24 hours by means of the tumor response form provided at site initiation.

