### **9.4.0 Statistical Analysis Plan**

#### **9.4.1. Efficacy Analysis**

A one-sample binomial test will be used to assess ORR. The null hypothesis that the ORR is less than or equal to 30% will be rejected if 13 or more participants have an ORR. The ORR will be

reported as a proportion with a 95% confidence interval. DOR and PFS will be reported as medians with 95% confidence intervals using Kaplan-Meier methods to account for censoring.

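### PFS in the evaluable set drops the earliest failures, and DOR has no rule for a responder who dies without progression

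*Combined protocol and SAP*

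**What the plan says.** **Analysis set.** The synopsis (Statistical Methods and Data Analysis) says "All efficacy analyses will be performed using all evaluable participants" and lists PFS under secondary efficacy analysis.
- Section 7.2.0 requires more than one cycle of drug and one CT with contrast or PET. Patients who miss more than 14 doses before the first evaluation at cycle 3 day 1 are not evaluable for efficacy.
- Section 9.2 speaks of efficacy in evaluable patients. It then defines response evaluability as at least one cycle, one CT, MRI or PET, and the same missed-dose limit. For toxicity it counts anyone with one dose.
- Section 3.1 ties the 31 evaluable patients to overall response.
- Section 9.4.1 names no set for PFS.

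**Endpoints (9.3.2).** "Duration of response is measured from date of documented tumor response, CR or PR, to date of disease progression". Next to it: "Progression-free survival is measured from date of study entry to date of progression or death, whichever occurs first".

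**Analysis.** Section 9.4.1: "DOR and PFS will be reported as medians with 95% confidence intervals using Kaplan-Meier methods to account for censoring". Synopsis: "DOR will be reported as median and range".

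**Follow-up.** Section 7.3.1: "CT with contrast will be performed every 12 weeks until disease progression, death, or end of study, whichever comes first". For patients who stop treatment before progression, the 12-week interval holds up to 15 months, and then "Thereafter, scan will be performed every 24 weeks until disease progression, or death, or the end of the study, whichever occurs first". Section 7.1.1 runs post-treatment assessments until "disease progression, death or study end, whichever comes first". Section 3.1 collects PFS and survival data from all subjects who do not withdraw consent, and Section 7.1.1 records the date of death.

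**The concern.** For PFS, the clock starts at study entry, but a patient joins the analysis only by reaching a later milestone. Someone who progresses clinically or dies in cycle 1, before any on-treatment imaging, never qualifies. The curve then begins with a stretch in which the included patients could hardly fail. Study entry itself is not defined: consent, registration and first dose are all candidates, and treatment may start up to 28 days after screening begins (7.1.1).

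For DOR, the plan names death as an event for PFS and omits it one definition earlier, without explanation. The same death would end PFS and be censored for DOR.

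DOR and PFS are the only measures of the secondary objective on duration of tumor control. The trial has one arm, so the medians are read on their own. Losing early failures and censoring responder deaths push in the same direction.

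**Working it through.** **1. The plan's own figures.** Exact binomial, n = 31, reject at 13 or more: P(X ≥ 13 | 0.30) = 0.1069 and P(X ≥ 13 | 0.50) = 0.859, against 10.69% and 85% stated. These reproduce, and nothing below changes them. With 35 patients planned for 31 evaluable, 35 − 31 = 4 are expected to be non-evaluable. The plan states no figure for DOR or PFS, so steps 3 to 7 rest on assumed shares.

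**2. Who leaves PFS.** Failures before day 28 (cycle 1 not completed) leave. If stopping counts as missed doses, so do failures before about day 41: there are 56 doses before cycle 3 day 1, and missing more than 14 leaves at most 41 taken. A patient dropped only for missed doses, without early failure, could move the curve either way. The direction stated here concerns early failures.

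**3. PFS, exponential.** Let k of the 4 non-evaluable patients be the earliest treated failures, so d = k/(31 + k). The evaluable curve reaches 50% where the all-treated curve is at 0.5(1 − d). The ratio of medians is ln[0.5(1 − d)]/ln(0.5).

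| k | d | Ratio |
|---|---|---|
| 0 | 0 | 1.000 |
| 1 | 1/32 | 1.046 |
| 2 | 2/33 | 1.090 |
| 3 | 3/34 | 1.133 |
| 4 | 4/35 | 1.175 |

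Section 9.5 counts 35 as consented, so each of the 4 who is never dosed lowers k by one.

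**4. PFS with progression dated at scans.** Scans fall at weeks 8, 20, 32 and so on. An assumed share of failures is clinical and dated exactly; the rest are dated at the next scan. Medians are in months, for all treated and then with clinical failures before day 28 or day 41 dropped.

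| True median | Clinical share | All treated | Early failures dropped |
|---|---|---|---|
| 6 | 25% or 50% | 7.36 | 7.36 |
| 9 | 25% or 50% | 10.12 | 10.12 |
| 12 | 25% or 50% | 12.88 | 12.88 |
| 6 | 75% | 6.52 | 7.36 (+13%) |
| 9 | 75% | 9.60 | 10.12 (+5%) |
| 12 | 75% | 12.68 | 12.88 or 13.04 (+2% or +3%) |

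The median often sits on a scan date and does not move, although the curve does. At a true median of 6 months with 50% clinical, 6-month PFS is 54.4% in all treated, and 57.3% or 58.6% after dropping. The plan does not say that it will report that rate.

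**5. DOR, exponential.** If a share s of response-ending events are deaths without progression and are censored, the ratio of medians is 1/(1 − s).
- s = 5%, 10%, 20%: 1.05, 1.11, 1.25.
- One death among 13 events: 1/(1 − 1/13) = 1.083. One among 15: 1.071.

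**6. DOR, Kaplan-Meier simulation.** Assumptions: 15 responders (about half of 31), true median 6 months, and follow-up after response uniform on 10.16 to 22.16 months. That is 12 to 24 months from entry, from one year of accrual and a cutoff one year later, less 8 weeks to response. With deaths as events the median is 6.0. With deaths censored it is 6.4, 6.7 and 7.5 for s = 5%, 10% and 20%. The median is unchanged in about 72%, 49% and 22% of runs.

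**7. Sampling error.** The approximate 95% factor for an exponential median is exp(±1.96/√events).
- DOR: 15 events give 0.60 to 1.66; about 12.5 events, the number seen by cutoff in step 6, give 0.57 to 1.74.
- PFS: even if all 35 patients had an event, 1.96/√35 = 0.331, giving 0.72 to 1.39.

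**The case against.** **The PFS set is stated.** A reader might infer from Sections 3.1, 9.2 and 9.4.1 that the plan leaves the set open, so that two analysts could choose differently and both follow the text. The documents do not support that. The synopsis puts every efficacy analysis in evaluable participants, Section 9.2 also speaks of efficacy in evaluable patients, Section 3.1 explains only the enrolment number, and Section 9.4.1 is silent rather than contrary. What stands is that the stated set suits response and biases a time-to-event curve that starts earlier.

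**Progression-only DOR is a legitimate definition.** A reader might call Section 9.3.2 an error. It is not; literally read, it can be applied. What stands is that the plan neither says the difference from PFS is intended nor says what happens to deaths. The published response criteria are cited for response categories, and nothing reproduced from them here covers DOR.

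**Progression is not found only at scheduled scans.** The 12- and 24-week intervals might suggest that it is. But Appendix 1 has a suspected-progression visit at any time, Section 7.1.1 wants clinical relapse documented when first detected, and patients are examined on day 1 of treatment cycles. This makes deaths without documented progression less frequent, not impossible: a responder can die of another cause.

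**The effect is small and assumed.** That is correct, as steps 4, 6 and 7 show. Nor does the undefined entry date require moving the PFS start to first dose; defining one date is enough.

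**Conclusion.** The point holds as a change that should be made, not one that threatens the trial. Followed as written, the plan removes early clinical failures from a PFS curve that starts at study entry, and it censors responder deaths in DOR that it counts in PFS. Each can only lengthen the median concerned or leave it unchanged, compared with all treated patients and with a progression-or-death DOR respectively.

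The size ranges from none to about 18% on the exponential PFS median, for 0 to 4 dropped failures, and from about 5% to 25% on the exponential DOR median, for death shares of 5% to 20%. These are illustrations, because the documents give no event rates. They lie within sampling error. DOR and PFS carry no hypothesis test, and the primary rule is unaffected. The mismatch between the synopsis and Section 9.4.1 on how DOR is reported is editorial.

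**What to change.** 1. **PFS set.** In the synopsis and 9.4.1, limit the evaluable set to ORR, and DOR to the responders in that set. Analyse PFS in all patients who received at least one dose, with the evaluable set as a sensitivity analysis. Define study entry as one date.
2. **DOR.** In 9.3.2, define DOR as the time from first documented CR or PR to progression or death from any cause, whichever is first, with other responders censored at the last adequate disease assessment. If progression-only DOR is intended, say so, state how deaths are handled, and report the progression-or-death version as well.
3. **Editorial.** Replace the synopsis reporting of DOR with the Kaplan-Meier median and 95% confidence interval of 9.4.1.

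The cost is text in the synopsis, 9.3.2 and 9.4.1, settled before analysis because it changes a population and an endpoint definition. No new data are needed: Section 9.2 already defines the at-least-one-dose set for toxicity, and progression and death dates are already collected. Patients who consent but are never dosed stay outside. The downside is possibly shorter reported DOR and PFS medians.

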#### **9.3.3. Exploratory Endpoints**

The influence of ibrutinib on T cell behavior and antitumor effect will be assessed using pre-therapy and post therapy flow cytometry measures of Th1 and Th2 at predetermined time points in therapy.

PDL1 and PDL2 copy number analysis on paraffin-embedded tissue sections will be assessed by FISH.

All patients undergoing any exploratory evaluations will be assessed for correlative analysis.

### **9.4.0 Statistical Analysis Plan**

#### **9.4.1. Efficacy Analysis**

A one-sample binomial test will be used to assess ORR. The null hypothesis that the ORR is less than or equal to 30% will be rejected if 13 or more participants have an ORR. The ORR will be

reported as a proportion with a 95% confidence interval. DOR and PFS will be reported as medians with 95% confidence intervals using Kaplan-Meier methods to account for censoring.

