## 3. STUDY DESIGN

### 3.1. Overview of Study Design

This is a multicenter, single-arm Phase 2 study to evaluate the efficacy and safety of single-agent ibrutinib in subjects with HL who have received at least 2 prior chemotherapy regimens and are ineligible for ASCT or have progressed after ASCT. Approximately 35 eligible subjects will be enrolled to have 31 evaluable subjects for overall response to treatment.

Subject participation will include a Screening Phase, a Treatment Phase, and a Posttreatment Phase (**Figure 1**). The Screening Phase will be up to 28 days and include a computed tomography (CT), or MRI scan and a positron emission tomography (PET) scan, prior to first dose. A formalin-fixed paraffin embedded tumor (FFPE) block must be sent to the central laboratory for confirmation of HL and biomarker analysis diagnosis. However, prior to enrollment, a report from the local laboratory that contains relevant data documenting HL diagnosis is acceptable.

[figure not shown]

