### **8.3 Withdrawal from Study**

A subject will be withdrawn from the study for any of the following reasons:

- Lost to follow-up
- Withdrawal of consent

If a subject is lost to follow-up, every reasonable effort must be made by the study site personnel to contact the subject and determine the reason for discontinuation/withdrawal. The measures taken to follow up must be documented. When a subject withdraws before completing the study, the reason for withdrawal is to be documented in the CRF and in the source document. Study drug assigned to the withdrawn subject may not be assigned to another subject. A subject who withdraws will not be replaced.

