### **9.2. Design**

This is a multicenter, single arm, single stage phase II study designed to estimate the efficacy of ibrutinib in evaluable patients with relapsed, refractory Hodgkin's lymphoma. A participant will be deemed response evaluable if he/she has completed at least one cycle of therapy, has at least one imaging study (CT, MRI or PET) and has not missed >25% of treatment dose (14 doses) prior to cycle 3 day 1. Any participant receiving at least 1 dose of ibrutinib will be considered evaluable for toxicity analysis.

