### **9.5. Sample Size Determination**

A study of 31 evaluable participants was deemed feasible. To accomplish this with an expected dropout not evaluable rate of 12%, a total sample population of 35 patients will be consented. We specified statistical power of 85% to distinguish a null hypothesis value of 30% against an alternative value of 50% assuming a binomial test of one proportion with a target, one-sided type error of 11%. Under these assumptions the null hypothesis will be rejected if there are 13 or more ORRs among the 31 participants.

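### The primary decision rule fixes 13 responses with no denominator; it matches the planned 11% exact test only at 29 to 31 evaluable patients, and no rule is given for other numbers

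*Combined protocol and SAP*

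**What the plan says.** Section 9.4.1 names a one-sample binomial test of ORR and then gives the decision rule: "The null hypothesis that the ORR is less than or equal to 30% will be rejected if 13 or more participants have an ORR". The analysis text of the synopsis also gives the count alone, with the attained alpha: "type I error = 10.69% the null hypothesis will be rejected if there are 13 or more ORRs".

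The denominator appears in Section 9.5 and in the matching synopsis entry on sample size: "Under these assumptions the null hypothesis will be rejected if there are 13 or more ORRs among the 31 participants". Section 9.5 sets the test up "with a target, one-sided type error of 11" percent, with 85% power for 50% against 30%.

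Four other statements determine how many patients enter the test:

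- Synopsis: "All efficacy analyses will be performed using all evaluable participants".
- Section 9.2: "A participant will be deemed response evaluable if he/she has completed at least one cycle of therapy". The same sentence adds an imaging requirement and a limit on missed doses. It sets no upper number.
- Section 3.1: "Approximately 35 eligible subjects will be enrolled to have 31 evaluable subjects for overall response to treatment".
- Section 8.3: "A subject who withdraws will not be replaced".

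**The concern.** The number evaluable is known only after treatment has started, so it may well not be 31. A count of 13 carries a different error rate at each denominator, and the plan does not say whether the count or the 11% target governs when they conflict.

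Two results show the conflict. With 13 responders of 33, the count rejects the null, but the exact one-sided p-value is 0.161, which misses the 11% target. With 12 of 28, the count does not reject, but the p-value is 0.103, which meets the target. Two competent analysts could draw opposite primary conclusions from the same data. In an open-label single-arm study the choice between readings would be made with the denominator and the responses already in view.

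**Working it through.** **Inputs.** Null rate 0.30, alternative 0.50, one-sided target 0.11, 31 evaluable, 13 responses, 12% non-evaluable and 35 patients (Section 9.5); attained alpha 10.69% (synopsis).

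**Formula.** For N evaluable and cut-off r, the rejection probability at true rate p is P(X ≥ r), with X ~ Binomial(N, p). Alpha uses p = 0.30 and power uses p = 0.50.

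**Step 1: the plan's own figure.** N = 31, r = 13 gives alpha 0.1069 and power 0.8595. Both stated figures reproduce.

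**Step 2: other denominators.** The table compares the fixed count of 13 with the smallest r whose tail at 0.30 is at most 0.11.

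| N | Alpha, r = 13 | Power, r = 13 | Exact 11% cut-off | Alpha | Power |
|---|---|---|---|---|---|
| 24 | 1.2% | 41.9% | 11 | 7.4% | 72.9% |
| 25 | 1.7% | 50.0% | 11 | 9.8% | 78.8% |
| 26 | 2.6% | 57.8% | 12 | 6.0% | 72.1% |
| 27 | 3.6% | 64.9% | 12 | 8.0% | 77.9% |
| 28 | 4.9% | 71.4% | 12 | 10.3% | 82.8% |
| 29 | 6.5% | 77.1% | 13 | 6.5% | 77.1% |
| 30 | 8.4% | 81.9% | 13 | 8.4% | 81.9% |
| 31 | 10.7% | 85.9% | 13 | 10.7% | 85.9% |
| 32 | 13.3% | 89.2% | 14 | 6.9% | 81.2% |
| 33 | 16.1% | 91.9% | 14 | 8.8% | 85.2% |
| 34 | 19.3% | 93.9% | 15 | 5.7% | 80.4% |
| 35 | 22.7% | 95.5% | 15 | 7.3% | 84.5% |
| 36 | 26.3% | 96.7% | 15 | 9.2% | 87.9% |

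The rules coincide only at N = 29, 30 and 31. At N = 34, 14 responses would give 11.03%, just over the target, so a strict reading needs 15.

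**Step 3: how often N falls outside that range.** Assume 35 treated and independent losses at the plan's 12%, so N ~ Binomial(35, 0.88), with mean 35 × 0.88 = 30.8. Then P(29 to 31) = 50.0%, P(32 or more) = 38.1%, P(28 or fewer) = 11.9% and P(34 or more) = 6.6%.

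**Step 4: how often the conclusion changes.** Sum over N of P(N) × |P(X ≥ 13) − P(X ≥ r_N)|, where r_N is the exact cut-off. Loss rates other than 12% are assumptions.

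| Loss rate | True ORR 30% | 40% | 50% |
|---|---|---|---|
| 10% | 4.7% | 9.9% | 5.3% |
| 12% | 3.6% | 8.0% | 4.8% |
| 15% | 2.9% | 7.3% | 5.5% |

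At 12% loss and a true ORR of 30%, the 3.6% is made up of 3.0% where only the count rejects and 0.6% where only the exact test does.

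**Step 5: averages over N.**

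| Loss rate | Fixed 13: alpha, power | Exact rule: alpha, power |
|---|---|---|
| 10% | 12.4%, 86.6% | 8.2%, 82.6% |
| 12% | 10.8%, 83.8% | 8.4%, 82.2% |
| 15% | 8.6%, 79.1% | 8.4%, 81.1% |

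The near-planned average at 12% combines opposite errors. Given N ≥ 32, the fixed count has alpha 15.4%. Given N ≤ 28, it has power 66.8%, against 79.9% for the exact rule.

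**The case against.** Read as a whole, the plan ties 13 to 31: Section 9.5 and the synopsis sample-size entry say so, and 10.69% is the exact tail at 13 of 31. Section 9.4.1 names a binomial test, which uses the realised number, so a reader could treat 13 as its worked value at the planned size. Nothing is miscalculated. The averaged error rates at 12% loss are close to plan, the most extreme alphas (34 or 35 evaluable) have probability 6.6%, and Section 9.1 describes the primary objective as estimation.

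The upper-tail probability also depends on 35 being treated. Section 9.5 counts 35 consented, whereas Section 3.1 counts 35 eligible and enrolled. If screening failures come out of the 35, fewer patients are treated. In addition, the no-replacement sentence in Section 8.3 covers withdrawals only, not patients who become non-evaluable for other reasons.

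Much of this stands. The gap is one of specification, it lies in what happens away from 31, and its average effect is small. It does not remove the point. The only rejection rule written in Section 9.4.1 is an explicit count, that section states no alpha, and naming the test does not displace the count that follows it. If fewer patients are treated, the mismatch moves to low N, where the fixed count loses power: with 33 treated (an assumption) and 12% loss, average power is 75.9%, against 80.5% for the exact rule.

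**Conclusion.** The concern holds. The design is valid at 31 evaluable patients, but the primary decision rule is incomplete at any other number and, applied as written, departs from the plan's own 11% target outside 29 to 31. The cut-offs and error rates at each N are exact and need no assumption beyond the binomial model. The probabilities of landing at a given N, the disagreement rates and the averages rest on the number treated and on independent losses at a constant rate. The chance of a changed conclusion is modest: 2.9% to 9.9% for 35 treated, losses of 10% to 15% and true response rates of 30% to 50%. It should be settled before the responses are known.

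**What to change.** In Section 9.4.1 and the synopsis, state that 13 responses is the cut-off for 31 evaluable participants, and that the null hypothesis is rejected if the exact one-sided binomial p-value at the realised number evaluable is at most 0.11, unrounded. Add the cut-offs:

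| Evaluable | Responses needed |
|---|---|
| 24–25 | 11 |
| 26–28 | 12 |
| 29–31 | 13 |
| 32–33 | 14 |
| 34–36 | 15 |

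In Section 9.5, say that the 85.95% power applies at 31, with about 77% to 86% for 27 to 35 evaluable and 72% to 79% for 24 to 26. Also make the 35 mean the same thing in Sections 3.1 and 9.5.

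Inserting the 31 into Section 9.4.1 would not be enough: it would still leave open what happens with fewer than 31, and with more unless the analysis set is capped.

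The cost is a few lines of text and no extra patients. With 35 treated, average power changes from 83.8% to 82.2% at 12% loss, from 86.6% to 82.6% at 10%, and from 79.1% to 81.1% at 15%. In return, alpha is at most 10.7% at every N from 24 to 36. The largest single cost of reading 11% strictly is at N = 34, where 15 responses give 80.4% power, against 88.5% for 14. If the sponsor prefers to tolerate 11.03% there, that should be written in advance.
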